7. PLANNED ANALYSIS

Safety analysis (refer to [Section 7.8](#)) will be performed by [REDACTED] and will be presented in Sections 15.1 to 15.4 of the CTR and in Appendix 16.2 and 16.1.13.1.

Tables and listings will be provided separately for the SRD part and BA part.

Statistical model-based analysis of PK endpoints will be performed by [REDACTED] and will be presented in Section 15.5 of the CTR and in Appendix 16.1.13.3.

Descriptive data analysis of PK endpoints and concentrations will be performed by the [REDACTED] at [REDACTED] and will be presented in Section 15.6 of the CTR and in Appendix 16.1.13.5.

Descriptive data analysis of PD/biomarker parameters will be performed by [REDACTED] and will be presented in Section 15.7 of the CTR and Appendix 16.1.13.6.

The format of the listings and tables will follow the BI standards (see BI-KMED-BDS-HTG-0045 ([7](#))) with the exception of those generated for PK-calculations following BI standards for PK/PD analysis ([8](#)).

The individual values of all subjects will be listed, sorted by dose group/placebo (SRD part) or treatment sequence (BA part), subject number and visit.

The listings will be included in Appendix 16.2 of the CTR.

For end-of-text tables, the set of summary statistics for non-PK and non-PD parameters is:

N	number non-missing observations
Mean	arithmetic mean
SD	standard deviation
Min	minimum
Median	median
Max	maximum

For analyte concentrations and PK parameters, the following descriptive statistics will additionally be calculated:

Nobs	number of observations
CV	arithmetic coefficient of variation
gMean	geometric mean
gCV	geometric coefficient of variation
P10	10th percentile
Q1	1st quartile
Q3	3rd quartile
P90	90th percentile

The data format for descriptive statistics of concentrations will be identical to the data format of the respective concentrations. The descriptive statistics of PK and PD parameters will be calculated using the individual values with the number of decimal places as provided by the evaluation program. Then the individual values as well as the descriptive statistics will be reported with three significant digits in the CTR.

Tabulations of frequencies for categorical data will include all possible categories available in CRF and will display the number of observations in a category, as well as the percentage (%). Percentages will be rounded to one decimal place and will be based on all subjects in the respective subject set whether they have non-missing values or not. The category 'missing' will be displayed only if there are actually missing values.

Exclusion of PK parameters

The ADS “ADPP” (PK parameters) contains column variables APEXC and APEXCO indicating inclusion/exclusion (APEXC) of a PK parameter and an analysis flag comment (APEXCO). All analyses based on the PKS will include parameters if they are not flagged for exclusion, that is APEXC is equal to “Included”.

Exclusion of PK concentrations

The ADS “ADPC” (PK concentrations per time-point or per time-interval) contains column variables ACEXC and ACEXCO indicating inclusion/exclusion (ACEXC) of a concentration and an analysis flag comment (ACEXCO). Exclusion of a concentration depends on the analysis flag comment ACEXCO. For example, if ACEXCO is set to ‘ALL CALC’, the value will be excluded for all types of analyses based on concentrations. If ACEXCO is set to ‘DESC STATS’ the value will be excluded from descriptive evaluations per planned time point/time interval. If ACEXCO contains the addition ‘TIME VIOLATION’ or ‘TIME DEVIATION’ the value can be used for further analyses based on actual times. If ACEXCO is set to ‘HALF LIFE’, the value will be excluded from half-life calculation (and, as a consequence, any calculation that relies on λ_z) only; the value is included for all other analyses.

Further details are given in *BI-KMED-TMCP-MAN-0014* “Noncompartmental Pharmacokinetic / Pharmacodynamic Analyses of Clinical Studies” ([6](#)) and *BI-KMED-TMCP-MAN-0010*: “Description of Analytical Transfer Files and PK/PD Data Files” ([9](#)).

7.1 DEMOGRAPHIC AND OTHER BASELINE CHARACTERISTICS

Only descriptive statistics are planned for this section of the report, based on the TS.

The data will be summarised by treatment group / treatment sequence and in total.

7.2 CONCOMITANT DISEASES AND MEDICATION

Frequency tables are planned for this section of the report, based on the TS.

Concomitant diseases will be coded using the latest version of the coding system of the Medical Dictionary for Drug Regulatory Activities (MedDRA). Medications will be coded using the latest version of the World Health Organization Drug Dictionary (WHO-DD). The coding version number will be displayed as a footnote in the respective output.

The diagnoses and medications will be listed. Patients without any concomitant diagnoses or concomitant therapies should be marked with a “No” in the respective column.

The relevance of the concomitant therapies to the evaluation of PK will be decided no later than at the RPM/DBLM.

7.3 TREATMENT COMPLIANCE

Section 4.3 of the CTP: *Compliance will be assured by administration of all trial medication in the study centre under supervision of the investigating physician or a designee. The measured plasma concentrations and/or urinary excretion of trial medication will provide additional confirmation of compliance.*

It is not intended to list the compliance separately. Any deviations from complete intake will be addressed in the RPM/DBLM (cf. TSAP [Section 6.2](#)) and described in the CTR.

7.4 PRIMARY ENDPOINTS

7.4.1 Primary analysis of the primary endpoints

SRD part: Please refer to [Section 7.8.1](#) for the description of the analysis of the primary endpoint.

BA part:

Section 7.3.1 of the CTP:

Primary analysis:

The primary endpoints (refer to [Section 5.1](#)) will be calculated according to the BI Standard (see BI-KMED-TMCP-MAN-0014 (6)).

The statistical model used for the analysis of the primary endpoints will be an analysis of variance (ANOVA) model on the logarithmic scale. That is, the PK endpoints will be log-transformed (natural logarithm) prior to fitting the ANOVA model. This model will include effects accounting for the following sources of variation: sequence, subjects within sequences, period and treatment. The effect 'subjects within sequences' will be considered as random,

whereas the other effects will be considered as fixed. The model is described by the following equation:

$$y_{ijkm} = \mu + \zeta_i + s_{im} + \pi_j + \tau_k + e_{ijkm},$$

where

y_{ijkm} = logarithm of response measured on subject m in sequence i receiving treatment k in period j ,

μ = the overall mean,

ζ_i = the i^{th} sequence effect, $i = 1, \dots, 6$

s_{im} = the effect associated with the m^{th} subject in the i^{th} sequence, $m = 1, 2, \dots, n_i$

π_j = the j^{th} period effect, $j = 1, 2, 3$

[figure not shown]
τ_k = the k^{th} treatment effect, $k = 1, 2, 3$

e_{ijkm} = the random error associated with the m^{th} subject in sequence i who received treatment k in period j .

where $s_{im} \sim N(0, \sigma_B^2)$ i.i.d., $e_{ijkm} \sim N(0, \sigma_W^2)$ i.i.d. and s_{im}, e_{ijkm} are independent random variables.

Point estimates for the ratios of the geometric means ($T1/T2$ and $T2/R$) for the primary endpoints (see TSAP [Section 5.1](#)) and their two-sided 90% confidence intervals (CIs) will be provided.

For each endpoint, the difference between the expected means for $\log(T)$ - $\log(R)$ (e.g. $\log(T1)$ - $\log(T2)$ or $\log(T2)$ - $\log(R)$) will be estimated by the difference in the corresponding adjusted means (Least Squares Means). Additionally their two-sided 90% confidence intervals will be calculated based on the residual error from the ANOVA and quantiles from the t -distribution. These quantities will then be back-transformed to the original scale to provide the point estimate and 90% CIs for each endpoint.

7.5 SECONDARY ENDPOINTS**7.5.1 Key secondary endpoints**

This section is not applicable as no key secondary endpoints have been specified in the protocol.

[figure not shown]
7.5.2 Other Secondary endpoints**Section 7.3.2 of the CTP:**

[figure not shown]
SRD part:

The secondary endpoints (refer to [Section 5.2.2](#)) will be analysed descriptively. [...]

BA part:

The secondary endpoints (refer to Section 5.2.2) will be calculated according to the BI Standard (see BI-KMED-TMCP-MAN-0014 (6)) and will be assessed statistically using the same methods as described for the primary endpoints.

7.7 EXTENT OF EXPOSURE

Descriptive statistics are planned for this section of the report based on the TS. The date and time of each drug administration will be listed for each subject.

7.8 SAFETY ANALYSIS

All safety analyses will be performed on the TS, separately for SRD and BA part.

If not stated otherwise, the safety results will be sorted by treatment group (SRD part) or by actual treatment (BA part).

The safety data for treated subjects who failed to complete the study (dropouts or withdrawals) will be reported as far as their data are available. All withdrawals will be documented and the reason for withdrawal recorded.

7.8.1 Adverse Events

The analyses of AEs will be descriptive in nature and will be based on BI standards as presented in “Analysis and Presentation of Adverse Event Data from Clinical Trials – Display Template” [BI-KMED-BDS-HTG-0041] ([10](#)) and [BI-KMED-BDS-HTG-0066] ([11](#)). All analyses of AEs will be based on the number of subjects with AEs and NOT on the number of AEs.

The analysis of AEs will be based on the concept of treatment emergent AEs. That means that all AEs occurring between first drug intake till 7 days after last drug intake will be assigned to

the randomised treatment. All AEs occurring before first drug intake will be assigned to ‘screening’ and all AEs occurring after last drug intake + 7 days will be assigned to ‘follow-up’ (for listings only). For details on the treatment definition, see [Section 6.1](#).

According to ICH E3 ([12](#)), in addition to Deaths and serious adverse events, ‘other significant’ AEs need to be listed in the clinical trial report. These will be any non-serious adverse event that led to an action taken with study drug (e.g. discontinuation or dose reduced or interrupted). An overall summary of adverse events will be presented.

The frequency of subjects with AEs will be summarised by treatment, primary system organ class (SOC) and preferred term (PT). Separate tables will be provided for subjects with serious AEs, for subjects with drug-related AEs, for subjects with drug-related serious adverse events, and for subjects with AESIs. In addition, the frequency of subjects with AEs will be summarised by treatment, worst intensity, primary system organ class (SOC) and preferred term (PT).

The SOCs and PTs will be sorted by frequency (within SOC). The MedDRA version number (most recent version) will be displayed as a footnote in the respective output.

According to the clinical study protocol, adverse events of special interest (AESI) will be analysed:

Section 5.2.6.1.4 of the CTP: *The following are considered as AESIs:*

- *Hepatic injury*
A hepatic injury is defined by the following alterations of hepatic laboratory parameters:
 - *An elevation of AST (aspartate transaminase) and/or ALT (alanine transaminase) ≥ 3 -fold ULN combined with an elevation of total bilirubin ≥ 2 -fold ULN measured in the same blood sample, or*
 - *Aminotransferase (ALT, and/or AST) elevations ≥ 10 fold ULN*

In addition, frequencies of subjects with non-serious AEs that had an incidence of $> 5\%$ for at least one treatment will be summarised by treatment, primary SOC and PT.

For disclosure of adverse events on EudraCT, additional information not included in a standard AE analysis will be performed. The following three entries will be created:

- Adverse Events per arm for disclosure on EudraCT
- Non-serious Adverse Events for disclosure on EudraCT
- Serious Adverse Events for disclosure on EudraCT

7.8.2 Laboratory data

The analyses of laboratory data will be descriptive in nature and will be based on BI standards [BI-KMED-BDS-HTG-0042] ([13](#)).

Laboratory data will be analysed qualitatively via comparison of laboratory data to their reference ranges. Values outside the reference range as well as values defined as possibly clinically significant will be flagged in the data listings.

Clinically relevant findings in laboratory data will be reported as baseline conditions (at screening) or as AEs (during the trial) if judged clinically relevant by the investigator, and will be analysed as such.

It is the investigator's responsibility to decide whether a lab value is clinically significantly abnormal or not (at the RPM at the latest).

Descriptive statistics of laboratory data including change from baseline will be calculated by planned time point based on the worst value of the subject at that planned time point (or assigned to that planned time point).

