4.1.5 Blinding and procedures for unblinding

4.1.5.1 Blinding

SRD part

The trial is designed single-blind. The treatments administered (active or placebo) will be blinded to subjects, but will be known to the investigators (outcome assessors). Only the current dose level will be known to the subjects due to the rising dose design.

A single-blind design is considered acceptable because the potential bias in this type of study seems to be low and according to study procedures it is assured that the investigator's knowledge of the next treatment does not influence the decision to enter a subject.

All trial data will be handled open label. This means that trial functions of the sponsor are unblinded (including clinical trial leader, data manager, statistician, bioanalyst, pharmacokineticist, pharmacometrist, drug metabolism scientist as well as dedicated personnel of the trial site).

Within the central ECG lab, the staff involved with interval measurements and assessments will be blinded with respect to the treatment and also with regard to the recording date and time as well as planned time points of the ECGs. The interval measurements for a given subject will be performed in a random and blinded sequence by a single technician.

Access to the randomisation schedule will be controlled and documented by a signed confidentiality statement, which will be stored in the TMF.

BA part

The BA part will be handled in an open fashion throughout (that is, during the conduct, including data cleaning and preparation of the analysis). This is considered acceptable because the potential for bias seems to be low and does not outweigh practical considerations. Emergency envelopes will not be provided, since the treatments (only active drug) of all subjects are known in this open-label trial.

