5.2.4 Safety laboratory parameters

For the assessment of laboratory parameters, blood and urine samples will be collected by the trial site at the times indicated in the [Flow Chart](#) after the subjects have fasted for at least 10 h (not on Day 1 of the SRD and BA part at 6 h after dosing). For retests, at the discretion of the investigator or designee, overnight fasting is not required. The parameters that will be determined are listed in Tables 5.2.4: 1 and [5.2.4: 2](#). Reference ranges will be provided in the ISF, Section 10.

Manual differential white blood cell count or urine sediment examinations will only be performed if there is an abnormality in the automatic blood cell count or in the urinalysis, respectively, and considered clinically relevant by the investigator.

Table 5.2.4: 1 Routine laboratory tests

Functional lab group	BI test name [comment/abbreviation]	A	E	B	C	D
Haematology	Haematocrit	X	X	X	--	X
	Haemoglobin	X	X	X	--	X
	Red Blood Cell Count/Erythrocytes	X	X	X	--	X
	Reticulocytes, absol.	X	X	X	--	X
	White Blood Cells/Leucocytes	X	X	X	--	X
	Platelet Count/Thrombocytes (quant)	X	X	X	--	X
Automatic WBC differential, relative	Neutrophils/Leukocytes; Eosinophils/Leukocytes; Basophils/Leukocytes; Monocytes/Leukocytes; Lymphocytes/Leukocytes	X	X	X	--	X
Automatic WBC differential, absolute	Neutrophils, absol.; Eosinophils, absol.; Basophils, absol. ; Monocytes, absol.; Lymphocytes, absol.	X	X	X		X
Manual differential WBC (if automatic differential WBC is abnormal)	Neut. Poly (segs); Neut. Poly (segs), absol.; Neutrophils Bands; Neutrophils Bands, absol.; Eosinophils/Leukocytes; Eosinophils, absol.; Basophils/ Leukocytes; Basophils, absol.; Monocytes/ Leukocytes; Monocytes, absol.; Lymphocytes/Leukocytes; Lymphocytes, absol.					
Coagulation	Activated Partial Thromboplastin Time Prothrombin time – INR (International Normalization Ratio) Fibrinogen	X	X	X	--	X
Enzymes	AST [Aspartate transaminase] /GOT, SGOT	X	X	X	X	X
	ALT [Alanine transaminase] /GPT, SGPT	X	X	X	--	X
	Alkaline Phosphatase	X	--	X	--	X
	Gamma-Glutamyl Transferase	X	--	X	--	X
	Glutamate Dehydrogenase (GLDH)	X	X	X	--	X
	Creatine Kinase [CK]	X	X	X	X	X
	Creatine Kinase Isoenzyme MB [only if CK is elevated]	X	X	X	X	X
	Myoglobin	X	X	X	X	X
	Lactic Dehydrogenase	X	X	X	X	X
	Lipase	X	--	--	--	X

A: parameters to be determined at Visit 1 (screening examination)

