6.2.3 Follow-up period and trial completion

For AE assessment, laboratory tests, recording of ECG and vital signs, and physical examination during the follow-up period, see Sections [5.2.2](#) to [5.2.6](#).

Subjects who discontinue treatment before the end of the planned treatment period should undergo the EoTrial Visit.

All abnormal values (including laboratory parameters) that are assessed as clinically relevant by the investigator will be monitored using the appropriate tests until a return to a medically acceptable level is achieved. (S)AEs persisting after a subject's EoTrial Visit must be followed until they have resolved, have been sufficiently characterised, or no further information can be obtained.

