6.7 BASELINE, TIME WINDOWS AND CALCULATED VISITS

SRD part: The baseline value is defined as the last measurement before first administration of trial medication (BI 474121 or Placebo).

BA part: The baseline value is defined as the last measurement before administration of trial medication in each treatment period (e.g. ptm -2:00).

For laboratory analysis, the last value on treatment will be defined as the last value during corresponding treatment period (usually 96:00h in first and second treatment period).

Adherence to time windows will be checked via the consistency check listings at the RPM.

Unscheduled measurements of laboratory data and vital signs data will be assumed to be repeat measurements of the most recent scheduled measurement (e.g. for follow-up or confirmation of a particular value). Therefore, unscheduled measurements will be assigned to the planned time point of the previous scheduled measurement.

There will be a centralised evaluation of the 12-lead ECG recordings of the SRD part at the time points and for the ECG recordings specified in [Table 6.7: 1](#) below:

Table 6.7: 1 Time schedule of 12-lead ECG recordings (SRD part)

Visit	Day	Planned time [hh:mm] (relative to drug administration)	Study phase	Central evaluation
1	-21 --1		Screening	NA
2	1	-01:00	Baseline	first ECG of each of the 3 triplicate baselines
		-00:45		
		-00:30		
		00:30		
		01:00		
		01:30		
		02:00		
		03:00		
		04:00		
		06:00		
		08:00		
		12:00		
	2	24:00		
		34:00		
	3	48:00	On-treatment	first single ECG of the triplicate
	4	72:00		
	5	96:00		
5	8-15		End-of-study examination	NA

At Screening and End-of-study examination ECG recordings are performed as single ECGs and will not be transferred to central ECG lab. Three triplicate ECGs will be recorded as the baseline before the first drug administration, but only the first ECG of each of the 3 baseline triplicates will be transferred to the database. At all other time points, 1 triplicate ECG will be recorded, but only the first single ECG of the triplicate will be transferred to the database. The baseline value of an ECG variable is defined as the mean of the ECG variable values prior to drug administration.

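### Laboratory change from baseline subtracts a last-value baseline from a worst-value post-dose result, so retests shift the descriptive mean towards worse; the shift is usually small and one rule on both sides removes it

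*SAP*

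**What the plan says.** Three SAP rules combine.

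- **Post-dose value (SAP 7.8.2).** Descriptive statistics by planned time, change from baseline included, are "based on the worst value of the subject at that planned time point (or assigned to that planned time point").
- **Baseline (SAP 6.7).** For the SRD part: "The baseline value is defined as the last measurement before first administration of trial medication". For the BA part: "The baseline value is defined as the last measurement before administration of trial medication in each treatment period", with the sample planned 2 h before dosing as the example.
- **Unscheduled values (SAP 6.7).** For laboratory data and vital signs, "unscheduled measurements will be assigned to the planned time point of the previous scheduled measurement".

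The protocol makes extra values foreseeable. Section 5.2.4 states: "For retests, at the discretion of the investigator or designee, overnight fasting is not required". Section 6.2.3 adds: "All abnormal values (including laboratory parameters) that are assessed as clinically relevant by the investigator will be monitored using the appropriate tests". In the SRD part, treatment "will be blinded to subjects, but will be known to the investigators (outcome assessors") (protocol 4.1.5.1).

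Vital signs are handled differently. SAP 7.8.3 takes the last value at each time point, which is the same kind of rule as the baseline. The laboratory analysis is declared descriptive.

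**The concern.** The change is a worst-of-n value minus a last-of-n value. The two selections lean in opposite directions. Taking the worst of several post-dose values can only move the result towards worse. Taking the last pre-dose value, when that value is a retest prompted by a high first result, moves the baseline towards normal. Both make the average change look like deterioration when the drug does nothing.

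Two further points follow from the text. SAP 7.8.2 does not exempt pre-dose times, so read literally the baseline row could show a worst value while the change uses the last one. And because a retest inherits the previous planned time, an SRD retest taken between the 72 h sample and the Day 8-15 visit would be tabulated at 72 h. It would displace the real 72 h value if it were worse, and it need not be fasting.

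At stake is the reading of mean laboratory changes in SRD groups of six active subjects. Protocol 7.3.4 commits to evaluating differences from baseline, and protocol 1.4.3 names muscle-injury markers as a safety measure.

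**Working it through.** The documents state no figure for this analysis, so there is none to reproduce. The check is a no-effect model.

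**Assumptions, none from the documents:** each value is a subject effect plus independent normal error; higher is worse; no drug effect; between-subject SD equal to within-subject SD; at most one retest. Results are in within-subject SD units, so one value has total SD √(1 + 1) = √2.

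**1. No retests.** Worst, last and scheduled coincide. Shift = 0.

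**2. Retest unrelated to the analyte's own value** (for example a repeat panel ordered for another parameter).
- Expected maximum of two independent standard normal values = 1/√π = 0.564; of three, 0.846.
- Each subject retested once post-dose gains +0.56 SD.
- If a share f is retested, the mean shift is 0.564 × f: 10% gives +0.06, 25% gives +0.14.
- Two of six active subjects: 2 × 0.564 / 6 = +0.19 SD for that group.
- Active minus placebo is 0.564 × (difference in shares): 0 if equal; 25% versus 10% gives 0.564 × 0.15 = +0.08; 50% versus 10% gives 0.564 × 0.40 = +0.23.

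**3. Retest only after a value above a limit, on both sides.** Let the limit be z total SDs above the mean and φ the standard normal density. The error in a first value above the limit averages φ(z)/(p√2), where p is the share above. The retest has mean error 0. Replacing the first value by the retest therefore lowers the mean baseline by p × φ(z)/(p√2) = φ(z)/√2.

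| Share above limit | z | Fall in baseline, φ(z)/√2 | Excess from worst-value rule, fresh baseline (simulated) | SAP rule in total (simulated) |
|---|---|---|---|---|
| 2.5% | 1.960 | 0.0584/1.414 = 0.041 | +0.001 | +0.04 |
| 5% | 1.645 | 0.1031/1.414 = 0.073 | +0.004 | +0.08 |
| 10% | 1.282 | 0.1755/1.414 = 0.124 | +0.01 | +0.13 |

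The simulations used 2 to 4 million subjects and agree with the formula to within about 0.002. Nearly all of the total comes from the baseline side: a high scheduled post-dose value is usually already the worst. With SD ratios from 0.5 to 2 and up to 16% retested, the post-dose excess alone stays between 0 and +0.04.

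**4. Where a retested baseline is possible.** The SRD flow chart draws set C on Day 1 before dosing. Set C holds AST, CK, myoglobin and LDH (protocol Table 5.2.4: 1). For these the last pre-dose value is normally that fresh sample, so only the fourth column applies. The BA flow chart draws set B before dosing in each period, so the same holds there. SRD analytes outside set C rely on the visit on Days -3 to -1 (ALT, for example) or on screening (glucose, for example). There the last value can be a triggered retest and the last column applies.

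**5. Effect of matching the rules, scenario 3.**
- Scheduled minus scheduled: 0.00.
- Last minus last: 0.00 if retesting is alike before and after dosing; but -0.04 / -0.07 / -0.12 if baseline is a single fresh sample and only post-dose values are retested.
- Scheduled post-dose minus the SAP 6.7 baseline: still +0.041 / +0.074 / +0.125.

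**Scale.** The standard error of a mean change in six subjects is √2/√6 = 0.58 SD.

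**The case against.** The strongest reply is that this is a conservative display convention in a descriptive analysis. The SAP deliberately takes the worst value for laboratory data and the last for vital signs. No test, power statement or primary endpoint depends on it, and flags and AE reporting already carry the safety message. SAP 6.7 describes unscheduled values as follow-up or confirmation, and protocol 6.2.3 ties extra tests to abnormal results, so the triggered case is the natural one and its post-dose contribution is tiny. SAP 7.8.2 also rests on a company standard that is not available here and may define both the worst value and the baseline handling.

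Most of this stands as a limit on size. A reader might infer that the worst-value rule moves mean CK and AST by +0.04 to +0.13 SD. The documents do not support that: those analytes have a fresh Day 1 pre-dose sample, which leaves about 0.00 to 0.01 SD. A reader might also infer a bias in the active-placebo comparison because the SRD investigator knows the treatment. That knowledge makes unequal retesting possible, but nothing in the documents shows it, and pooled placebo is summarised by the same rule.

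What the reply does not remove is the mismatch. No passage reconciles the two rules, and discretionary retests unrelated to the analyte's value remain possible under protocol 5.2.4. The baseline-row discrepancy is a matter of reading, since SAP 6.7 may be meant to govern; it is an ambiguity and not a demonstrated error.

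**Conclusion.** The point holds, as a minor one. As written, the laboratory change from baseline is shifted towards worse wherever retests exist. The size depends on the circumstances set out in the working, and every figure there rests on assumed retest rates, normal values and an assumed SD ratio. Even +0.13 SD is less than a quarter of the standard error of a six-subject mean change (0.13/0.58 = 0.22), and two unrelated retests among six subjects amount to about a third (0.19/0.58 = 0.33). For analytes that can be abnormal in either direction, such as sodium or potassium, the direction is undetermined until the worst value is defined; the available SAP text does not define it.

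**What to change.** In SAP 6.7 and 7.8.2, apply one selection rule to baseline and post-dose values for the laboratory descriptive statistics and change from baseline:

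- preferably the scheduled sample on both sides, with the last scheduled pre-dose sample as baseline and a retest used only if the scheduled sample is missing or invalid; or
- the last value on both sides, as SAP 7.8.3 already does for vital signs. This is second choice, because it gives zero only if retesting is alike before and after dosing.

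Changing the post-dose rule alone is not enough, since most of the triggered-retest shift sits in the baseline. Use the same baseline value in the baseline row. Keep the worst value, retests included, for the reference-range and possibly-clinically-significant flags and the listings, and define it per analyte or cite where it is defined.

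The cost is a sentence or two in the SAP and a selection rule in the program. The mean tables become slightly less conservative; extreme values remain visible in the flags and listings.
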